2. Patients will be transferred to the CTICU intubated and on a propofol infusion and/or dexmedetomidine (Precedex) from the operating room. Both meds are used SOC.
3. Upon CTICU arrival, the patients surgeon and CTICU intensivist will determine if patient is able to proceed with fast-track extubation. Determination of continued eligibility based on the post-recruitment pre-randomization exclusion criteria will be determined by a member of the study team. Eligible patients will be randomized, investigational pharmacy will be contacted for study drug and within 30 minutes of the ICU admission, propofol will be discontinued. Precedex may be continued per clinical discretion.
4. The participant will be randomized to receive Sugammadex or placebo. The enrolled patients will be assigned to the study and control arms in a 1:1 ratio.
5. IDS will provide the Sugammadex (2mg/kg) vs. Placebo in a syringe. A qualitative train-of-four measurement will be obtained. The administration of the study drug and placebo compounds will be performed by CTICU nurses who will receive the drugs in a blinded fashion from the departmental research pharmacy. The study drug will be supplied by Merck.
6. The clinical care provider has the discretion to determine the appropriate ventilation settings on a case-by-case basis, in accordance with the suggestion that patients will be initiated on SIMV rate of 14 with 60% FiO₂, tidal volumes 8-10 ml/kg and PEEP of 7.
7. Ten minutes after the drug administration, if the patient can lift their head and remains hemodynamically stable, the patient will be switched to CPAP mode of ventilation for 30 minutes. At the end of the CPAP trial tidal volumes, Rapid Shallow Breathing Index (RSBI) and ABG will be assessed. The patient will be extubated if he/she is not hypoxic/ hypercarbic, has RSBI<100 and has TV >300 cc.
8. If a patient fails the 30-minute CPAP criteria, the ICU intensivist will be immediately notified. Every attempt will be made to correct the underlying cause of CPAP failure, and a prompt reassessment will be made as deemed appropriate by the intensivist to reattempt CPAP versus continuing controlled mechanical ventilation.

Study participation will end when the patient is successfully extubated. AE assessment will be performed in the period immediately following extubation.

5. Genetic Testing N/A

6. **Subject Population:** Provide a detailed description of the types of human subjects who will be recruited into this study.

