- e.) Unrelated: Adverse event is clearly not related to investigational procedures(s)/agent(s).

4. Plan for Grading Adverse Events:

The following scale will be used in grading the severity of adverse events noted during the study:

1. Mild adverse event
2. Moderate adverse event
3. Severe

5. Plan for Determining Seriousness of Adverse Events:

Serious Adverse Events:

In addition to grading the adverse event, the PI will determine whether the adverse event meets the criteria for a Serious Adverse Event (SAE). An adverse event is considered serious if it results in any of the following outcomes:

1. Death;
2. A life-threatening experience in-patient hospitalization or prolongation of existing hospitalization;
3. A persistent or significant disability or incapacity;
4. A congenital anomaly or birth defect; OR

5. Any other adverse event that, based upon appropriate medical judgment, may jeopardize the subject's health and may require medical or surgical intervention to prevent one of the other outcomes listed in this definition.

An adverse event may be graded as severe but still not meet the criteria for a Serious Adverse Event. Similarly, an adverse event may be graded as moderate but still meet the criteria for an SAE. It is important for the PI to consider the grade of the event as well as its "seriousness" when determining whether reporting to the IRB is necessary.

Only the following adverse events will be tracked. These AE's will trigger an immediate DSMB review; any incidence of anaphylaxis; unexplained hypotension requiring initiation of pressors; cardiac pacing within 5 minutes of drug administration; tachycardia, bradycardia or onset of atrial fibrillation; or increases in chest tube output considered clinically significant by the critical care team. The DSMB will be notified within 2 business days of determination by telephone or email. A written report will be provided within 7 days of the determination. Any incidents meeting SAE criteria will be reported per the IRB reporting policy.

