If the DSMB determines that study drug may be causing an increase in adverse events, the study will be suspended until the DSMB can fully review the events and make a recommendation in consultation with the Yale Human Investigations Committee. The local Merck research representative will also be notified about the events (within 2 business days in case of any serious adverse events). If the data monitoring board and/or IRB view that the study is unsafe, the study will be discontinued.

6. Plan for reporting UPIRSOs (including Adverse Events) to the IRB

The principal investigator will report the following types of events to the IRB:

Any incident, experience or outcome that meets ALL 3 of the following criteria:

1. Is unexpected (in terms of nature, specificity, severity, or frequency) given (a) the research procedures described in the protocol-related documents, such as the IRB-approved protocol and informed consent document and (b) the characteristics of the subject population being studied; AND
2. Is related or possibly related to participation in the research (*possibly related* means there is a reasonable possibility that the incident, experience, or outcome may have been caused by the procedures involved in the research); AND
3. Suggests that the research places subjects or others at greater risk of harm (including physical, psychological, economic, legal, or social harm) than was previously known or recognized.

Unanticipated Problems Involving Risks to Subjects or Others (UPIRSOs) may be medical or non-medical in nature, and include – but are not limited to – *serious, unexpected, and related adverse events and unanticipated adverse device effects*. **Please note** that adverse events are reportable to the IRB as UPIRSOs **only** if they meet all 3 criteria listed above.

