These UPIRSOs/SAEs will be reported to the IRB in accordance with IRB Policy 710, using the appropriate forms found on the website. All related events involving risk but not meeting the *prompt* reporting requirements described in IRB Policy 710 should be reported to the IRB in summary form at the time of continuing review. If appropriate, such summary may be a simple brief statement that events have occurred at the expected frequency and level of severity as previously documented. In lieu of a summary of external events, a current DSMB report can be submitted for research studies that are subject to oversight by a DSMB (or other monitoring entity that is monitoring the study on behalf of an industry sponsor).

7. Plan for reporting adverse events to co-investigators on the study, as appropriate the protocol's research monitor(s), e.g., industrial sponsor, Yale Cancer Center Data and Safety Monitoring Committee (DSMC), Protocol Review Committee (PRC), DSMBs, study sponsors, funding and regulatory agencies, and regulatory and decision-making bodies.

For the current study, the following individuals, funding, and/or regulatory agencies will be notified (choose those that apply):

- All Co-Investigators listed on the protocol.
- Study Grantor (Merck)
- Other Data Safety Monitoring Board (DSMB)
- Yale University IRB

The principal investigator [name] will conduct a review of all adverse events upon completion of every study subject. The principal investigator will evaluate the frequency and severity of the adverse events and determine if modifications to the protocol or consent form are required.

See also DSMB charter attached.

13. Statistical Considerations: Describe the statistical analyses that support the study design.

Variables/Time Points of Interest

The primary outcome is the time to extubation, which will be the duration from arrival to the ICU to the extubation time.

Proposed statistical test/analysis: Positively skewed variables will be log-transformed prior to hypothesis testing. For the primary outcome, a two-sided Student's t-test will be used to compare

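### In the available text, a death, other SAE or serious respiratory event outside the closed AE list has no dated notice to the DSMB; one amended sentence would supply it

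*Protocol*

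**What the plan says.** Protocol, Section I, 12, item 5 defines an SAE, with death as the first criterion, and then sets the DSMB trigger: "Only the following adverse events will be tracked. These AE's will trigger an immediate DSMB review; any incidence of anaphylaxis". The rest of the list is unexplained hypotension needing pressors, pacing within 5 minutes of study drug, tachycardia, bradycardia or new atrial fibrillation, and clinically significant chest tube output. The clock comes next: "The DSMB will be notified within 2 business days of determination by telephone or email", with a written report in 7 days. SAEs as a class are then sent elsewhere: "Any incidents meeting SAE criteria will be reported per the IRB reporting policy".

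Still in item 5, the drug supplier's local representative "will also be notified about the events (within 2 business days in case of any serious adverse events". Under item 6 an adverse event is reportable to the IRB as an unanticipated problem only "if they meet all 3 criteria listed above" (unexpected, related, and suggesting greater risk). Related events that miss the prompt-reporting rules "should be reported to the IRB in summary form at the time of continuing review". Item 7 names the DSMB among those to be notified but gives no deadline, has the PI review all adverse events after each subject, and points to an attached DSMB charter. Item 1 requires safety reviews at least every 3 months and lets the PI, the IRB or the DSMB stop the study.

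The SAP (Adverse Experience Reporting) has the DSMB meet monthly on serious events. Its own trigger list is shorter than the protocol's and also names neither death nor any respiratory event.

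In the Research Plan (Section I, 4, step 7), ten minutes after study drug a stable patient who can lift the head moves on: "the patient will be switched to CPAP mode of ventilation for 30 minutes". Extubation can follow. Participation ends at successful extubation, and "AE assessment will be performed in the period immediately following extubation".

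**The concern.** The protocol defines seriousness and then builds its fastest DSMB route around a list that does not use the definition. The list covers allergic, haemodynamic, rhythm and bleeding events. It has nothing respiratory, yet the pathway can bring a patient from study drug to an extubation decision in about 10 + 30 = 40 minutes. Respiratory failure or early reintubation is therefore a plausible serious harm of this pathway, and it is the kind of event that can occur with no listed event beside it.

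The DSMB's determination is what suspends the study under item 5. If an isolated off-list SAE occurs, staff who follow the written rule owe the DSMB no notice by any stated date. The DSMB may first consider the event at its next scheduled meeting.

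**Working it through.** **Step 1. Routes by which an off-list SAE can reach the DSMB, or someone who can act.**

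| Route | Covers an off-list SAE? | Time limit |
|---|---|---|
| Protocol 12, item 5: immediate DSMB review | No, listed events only | 2 business days; report in 7 days |
| Protocol 12, item 7: notification list | Yes | None stated |
| SAP: DSMB meeting | Yes | Monthly |
| Protocol 12, item 1: safety review with DSMB | Yes | At least every 3 months |
| Protocol 12, item 6: IRB | Prompt only if the criteria are met | Otherwise continuing review |
| Protocol 12, item 7: PI review | Yes, but this is the PI | After each subject |

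No row gives the DSMB a dated, expedited notice of an off-list SAE.

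**Step 2. Inputs for the delay.** The number randomised is 90, that is 45 per group (Section I, 13). That figure reproduces: a two-sample t-test with difference 2 h, SD 2.89 h, two-sided alpha 0.05 and 90% power needs 44.86, so 45 per group, with power 0.901. Nothing below changes it.

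The accrual period is 2 years (Section I, 2), so the rate is 90/104 = 0.865 per week. The stated 3 per week would fill the trial in 90/3 = 30 weeks, which fits neither the protocol's 2 years nor the SAP's 1 year, and the SAP reports slow recruitment. The slower rate is the base case.

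**Step 3. Patients randomised before the DSMB is reached = weekly rate × weeks.**

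- Monthly meeting: 365.25/(12 × 7) = 4.35 weeks. Maximum 0.865 × 4.35 = 3.76. Average is half of this, 1.88, if events fall at random between meetings.
- Notice in 2 business days: 0.4 of a working week, 0.865 × 0.4 = 0.35. Across a weekend (4 calendar days), 0.865 × 4/7 = 0.49.
- Written report in 7 days: 0.865 × 1 = 0.87.

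Monthly meeting against notice: 3.76 − 0.35 = 3.4 at most, 1.88 − 0.35 = 1.5 on average. Against the written report, which is closer to review than bare notice is: 3.76 − 0.87 = 2.9 at most, 1.88 − 0.87 = 1.0 on average.

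**Step 4. Sensitivity.**

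| Rate per week | Monthly, max (average) | 2 business days | 7-day report |
|---|---|---|---|
| 0.865 (90 over 2 years) | 3.8 (1.9) | 0.35 to 0.49 | 0.87 |
| 1.73 (90 over 1 year) | 7.5 (3.8) | 0.69 to 0.99 | 1.7 |
| 3 (stated) | 13 (6.5) | 1.2 to 1.7 | 3 |

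If only the protocol's 3-month minimum were kept, 0.865 × 13 = 11.25 at most, 5.6 on average.

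**Step 5. Frequency.** The documents give no off-list SAE rate. As an assumption only, 0.5% to 5% of 90 patients gives 0.45 to 4.5 events, and 1 − (1 − p)^90 gives a 36% to 99% chance of at least one. That range is too wide to say how often the gap would matter. It serves only to bound the extra workload.

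**The case against.** The strongest objection is that a DSMB charter is attached to the protocol and is the natural home for triggers and timelines. The charter, the IRB policy and the opening part of the SAP were not available, so an SAE trigger may already exist. That stands, and it makes the point conditional. It does not remove the word *Only* from item 5, and staff will read item 5.

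The list also follows the drug's main recognised risks, and a targeted trigger is a legitimate choice. After cardiac surgery an all-SAE trigger will send the DSMB some events caused by the operation. That is a real but small cost.

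The two-business-day clock runs from a determination and sits under a heading on determining seriousness, so it could be stretched to SAEs. The more natural reading ties it to the list just before it, and the following sentence sends SAEs to the IRB policy.

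Three stronger readings are tempting, and the documents support none of them:

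- *SAEs go unrecorded or never reach the DSMB.* Adverse events are monitored and attributed, the PI judges seriousness and reviews every subject, and the SAP has the DSMB discuss serious events monthly.
- *Faster notice spares patients.* Notice does not pause randomisation. Suspension follows only if the DSMB determines that study drug may be increasing adverse events, which one event need not show.
- *The supplier hears of every SAE before the DSMB does.* The supplier sentence may refer only to events already under DSMB review, and its *also* may imply that the DSMB is told too. The comparison is ambiguous, and nothing here rests on it.

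**Conclusion.** The point holds as a low-cost improvement that should be made. It is not a fatal flaw. In the available text the expedited DSMB route is closed to deaths, other SAEs and respiratory events that come without a listed event.

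In the base case the change brings DSMB awareness forward by about 1.0 to 1.5 randomisations on average and 2.9 to 3.4 at most. This rests on 90 patients spread evenly over 2 years, monthly meetings held as the SAP says, and no earlier word to the DSMB from the PI, the IRB or the undated notification.

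Two limits remain. Many deaths would involve a listed event such as hypotension or bradycardia, so the gap is mainly about isolated respiratory events. And a reader might infer that the change captures all reintubations. It does not, because assessment stops shortly after extubation and later reintubation stays outside it.

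**What to change.** In Protocol, Section I, 12, item 5, delete *Only* and add to the list: *any death or other event after randomisation that meets the SAE criteria above, including respiratory failure or reintubation within the AE assessment period*. Use the existing path of DSMB notice in 2 business days and a written report in 7 days. Mirror the wording in the SAP under Adverse Experience Reporting. Check the DSMB charter first; if it already has an SAE trigger, align both documents with it instead.

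The cost is one amended sentence in each document, plus a few extra DSMB notices, some for SAEs due to surgery (0.45 to 4.5 over the trial under the assumed 0.5% to 5% rate). Sample size, alpha, power, assessment period and committee are unchanged.

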4. Determination that the patient will require prolonged mechanical ventilation possibly requiring muscle relaxation based on the intraoperative course and clinical judgment of the study PI or collaborating intensivists.
5. Intraoperative hypoxia or on arrival to the ICU. (Please see Study Flowchart).
6. Cardiac arrest
7. Sudden arrhythmia (Ventricular tachycardia runs/sudden bradycardia with improper pacemaker detection/function) precluding fast-track extubation protocol.
8. Need for two or more inotrope initiation precluding fast-track protocol. Only a single vasopressor/inotrope may be initiated without excluding the subject.
9. Postoperative ST changes.

10. A positive standard of care pregnancy test during your pre-operative evaluation

9. How will **eligibility** be determined, and by whom?

Eligibility at pre-op and post-op will be based on protocol specific inclusion and exclusion criteria and will be determined by the PI or Sub-I's in collaboration with the ICU attending physician

10. **Risks:** Describe the reasonably foreseeable risks, including risks to subject privacy, discomforts, or inconveniences associated with subjects participating in the research.

Sugammadex is generally safe and well tolerated. Potential risks associated with sugammadex are: hypersensitivity, including anaphylaxis/anaphylactic shock – previous trials suggest this risk is small. Cardiac arrhythmias including bradycardia & tachycardia where intervention is rare and responsive to usual treatment. Other reported risks include nausea, vomiting, constipation.

Bleeding was originally thought to be a side effect, but studies have since showed that Sugammadex falsely elevates the PTT without increasing bleeding risk. (see reference on last page.)

11. **Minimizing Risks:** Describe the way the above-mentioned risks will be minimized.

Patients will all be in a critical care environment and monitored very closely including: blood pressure, heart rate, and chest tube output will be tracked from arrival to the CTICU until extubation per ICU protocol. Subtle changes in the patient's hemodynamic status are easily seen and treated if necessary.

12. **Data and Safety Monitoring Plan:** Include an appropriate Data and Safety Monitoring Plan (DSMP) based on the investigator's risk assessment stated below. (Note: the HIC will make the final determination of the risk to subjects.)

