**Adverse Experience Reporting:** Throughout the duration of the study, researchers will adhere to good clinical practice and the guidelines of the institution. Patient vitals will be continuously monitored during and after the administration of the test drug. A data and safety monitoring board (DSMB) consisting of the head nurse and a senior critical care staff will meet monthly to discuss any serious events. Any incidence of anaphylaxis or unexplained hypotension requiring initiation of pressors or cardiac pacing within 5 minutes of drug administration will be reported and evaluated. Increases in chest tube output considered clinically significant by the critical care team will be noted. Any of these adverse events will trigger an analysis by the DSMB. If the DSMB determines that study drug may be causing an increase in adverse events, the study will be suspended until the DSMB is able to fully review the events and make a recommendation in consultation with the Yale Human Investigations Committee. The local Merck research

representative will also be notified about the events. If the data monitoring board and/or institutional review board (IRB) view that the study is unsafe, the study will be discontinued.

**Specific Safety Events to Be Reported During Manuscript Preparation:** For manuscript preparation, the rates of hypotension, anaphylaxis, and bleeding (i.e. Chest Tube output) will be reported and compared between active and placebo groups.

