**Protocol Amendments:**

Three changes were made to the protocol within the first year of initiation to generalize the inclusion criteria due to slow recruitment rates:

1. Originally the trial's inclusion criteria was patients undergoing isolated coronary artery bypass grafting. It was expanded to allow for coronary artery bypass grafting (CABG), aortic valve replacement (AVR) or coronary artery bypass grafting and aortic valve replacement (CABG and AVR).
2. The exclusion criteria for postoperative temperature was changed from 36.2° C to 35.5° C.
3. Low dose pressors infusion was allowed as long as it did not preclude fast track protocol as adjudicated by the clinical team that was blinded to the arm allocation.

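### Hypotension is tracked only if a pressor is started, so a fall treated by raising a pressor already running is neither counted nor a DSMB trigger

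*Protocol*

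**What the plan says.** Protocol, Section I, item 12 (Data and Safety Monitoring Plan), part 5, sets a closed list: "Only the following adverse events will be tracked". It attaches a consequence to that list: "These AE's will trigger an immediate DSMB review; any incidence of anaphylaxis", followed by "unexplained hypotension requiring initiation of pressors; cardiac pacing within 5 minutes of drug administration" and then heart-rate, rhythm and chest-tube items. The only blood-pressure item is the one that needs a pressor to be started.

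The SAP, under Adverse Experience Reporting, says: "Any incidence of anaphylaxis or unexplained hypotension requiring initiation of pressors or cardiac pacing within 5 minutes of drug administration will be reported and evaluated". Such events lead to a DSMB analysis. A separate SAP paragraph on safety events for the manuscript says that hypotension rates will be compared between arms, with no definition of hypotension.

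On eligibility, the protocol's exclusions between recruitment and randomisation (Section I, item 8, exclusion 8) state: "Only a single vasopressor/inotrope may be initiated without excluding the subject". The SAP's Protocol Amendments, item 3, record that "Low dose pressors infusion was allowed as long as it did not preclude fast track protocol". Neither document mentions an increase in a running infusion as an event.

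**The concern.** The eligibility rule and the event definition do not fit together. Patients may reach study drug with a pressor already running, but the event is defined by starting one. The same unexplained fall in pressure, with the same need for more support, is an event in a patient off pressors and may not be one in a patient on them.

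Two uses depend on the definition. The first is the DSMB trigger: the protocol makes suspension depend on the DSMB's judgement of whether the drug may be increasing adverse events, and episodes that are not logged cannot prompt that review. The second is the comparison of hypotension between arms, in a trial whose title claims both efficacy and safety and whose Background notes reports of hypotension with this drug.

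**Working it through.** **Plan's own figure.** The documents give no figure for hypotension, so there is none to reproduce for this point. The sample size gives the denominator. With SD 2.89 h, a 2 h difference, two-sided alpha 0.05 and 90% power, the normal approximation gives 2 × (1.960 + 1.282)² × 2.89² / 2² = 43.9, so 44 per arm. The noncentral t solution is 44.86, so 45 per arm, with power 0.901. The stated 45 per group reproduces and is not affected by this point.

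**Reading the list against eligibility.**

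| At dosing | Response to unexplained hypotension after study drug | Tracked event? |
|---|---|---|
| No pressor | Pressor started | Yes |
| Inotrope alone | First pressor started | Yes |
| One pressor running | Second pressor added | Probably, since an agent is started |
| One pressor running | Running infusion increased | No |

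The gap is the last row.

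**Size, if the tracked event is used for the between-arm comparison.** Let q be the share of patients on a pressor at dosing. Assume that q and the risk are the same for patients on and off a pressor within each arm, that q is equal in both arms, and that every episode in patients on a pressor is handled by raising the infusion. Then

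counted risk = true risk × (1 − q).

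Neither q nor the risks are in the documents. With assumed true risks of 20% and 5% and 45 per arm:

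| q | Counted risks | Expected counted events | Difference | Risk ratio | Power, Fisher's exact test |
|---|---|---|---|---|---|
| 0 | 20% vs 5% | 9.0 vs 2.25 | 15 points | 4 | 0.48 |
| 0.2 | 16% vs 4% | 7.2 vs 1.8 | 12 points | 4 | 0.34 |
| 0.4 | 12% vs 3% | 5.4 vs 1.35 | 9 points | 4 | 0.20 |
| 0.6 | 8% vs 2% | 3.6 vs 0.9 | 6 points | 4 | 0.07 |

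At 30% vs 10% the power over the same values of q is 0.58, 0.45, 0.31 and 0.15. At 10% vs 5% it is 0.06 or lower throughout.

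If only a share s of the episodes in patients on a pressor is handled by an increase, the factor becomes 1 − q × s. For example, q = 0.4 with s = 0.5 gives 0.8, the same as the row for q = 0.2.

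**Ratio.** With equal q the factor cancels, so the ratio is unchanged. If q differs by chance, the ratio is multiplied by (1 − q active)/(1 − q placebo). With 0.5 vs 0.3 that is 0.5/0.7 = 0.71, and a true ratio of 4 would appear as about 2.9.

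**The case against.** The strongest objection is that the pressor condition belongs to the tracked list and the DSMB trigger, whereas the between-arm comparison sits in its own SAP paragraph without that condition. Blood pressure is followed until extubation, so a broader count could be made. This stands. A reader might infer that the reported rate is bound to be too low, but the text leaves it undefined. Under-counting is a likely reading because no other definition exists. No blood-pressure threshold is given, and a broader count chosen later would not be pre-specified.

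A reader might also infer that a finding of no excess would be produced by the definition. The arithmetic does not support that: under equal risk the ratio does not move, and at 20% vs 5% power is only 0.48 even with complete counting. What shrinks is the number of events, the absolute difference and the power.

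Backstops exist. Serious events go to the IRB, safety reviews take place at least every three months, and the investigator reviews adverse events after each subject. They soften the gap without closing it: the listed item has no seriousness condition, and the reviews work from the same closed list. The DSMB charter is said to be attached but is not among the documents, so it may say more.

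The group affected may be small. The amendment speaks of low-dose infusions, and exclusion 8 also covers inotropes. The documents do not show that these patients have the least haemodynamic reserve.

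Finally, it is tempting to extend the point to pacing. It does not carry over. The protocol's pacing item has no condition that the pacing be new, so a patient already paced could be counted, and bradycardia is listed separately. The SAP sentence can be read as requiring pacing to be started. That is a wording difference to reconcile, not the same gap.

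**Conclusion.** The gap holds on the documents' own wording. In patients dosed while on a pressor, unexplained hypotension treated by raising that infusion is neither a tracked adverse event nor a DSMB trigger. For the DSMB trigger this needs no numerical assumption.

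For the between-arm comparison the conclusion is conditional. If the tracked event is used, events are under-counted in both arms, and the absolute difference and power fall. The risk ratio is unchanged when risk and pressor use are as assumed above. The size cannot be fixed from the documents; the table shows a range under assumed inputs and takes the worst case for how episodes are managed. The primary outcome and sample size are untouched. This is worth correcting because it concerns safety ascertainment and costs little.

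**What to change.** In the protocol's tracked-event list and in the SAP's Adverse Experience Reporting paragraph, define the event as unexplained hypotension requiring a pressor to be started, another to be added, or an increase in one already running at study drug administration. State in the SAP that the same definition is used for the comparison between arms. Record pressor agent and rate at dosing, and show hypotension by arm separately for patients on and off a pressor at that time. Reconcile the pacing wording between the two documents in the same edit.

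The cost is about one sentence in each document, one item of baseline data and a small table. The documents do not say that infusion rates are already captured for the study, so a field may have to be added. There will be a few more events to review, and the hypotension rate may look less favourable. Some increases may be routine titration; keeping the condition that the hypotension be unexplained and require the increase limits this. The change affects what is counted, not eligibility or any treatment rule.
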